6.5 Visit 6 (Final Visit or Early Termination) – Day 92 (±5 days)

The assessments/procedures listed for Visit 6 (Final Visit) are to be completed by all subjects regardless of whether they complete the entire study or prematurely withdraw from the study. If the Final Visit is performed before Day 92 due to early termination of the subject, every effort should be made to perform the clinical evaluations as follows, especially the blood sampling for hematology, serum chemistry, and urinalysis, and the ECG. Assessments/procedures will include the following:

- Record weight (Section 9.4).
- The study evaluator will perform the TNmAS-MAL (Section 8.1).
- Record vital sign measurements, including BP, heart rate, respiratory rate, and body temperature (Section 9.2).
- Collect blood and urine samples for hematology, serum chemistry, and urinalysis (Section 9.5). Subject should be fasting if possible.
- Perform a standard 12-lead ECG (Section 9.6.1).
- Collect a urine sample for pregnancy testing for women of childbearing potential (Section 7.8).
- Collect unused study medication, assess compliance, and study drug accountability (Section 7.9).

[figure not shown]
- Administer the C-SSRS (Section 9.6.3).
- Administer the EDSS (Section 8.4).
- Administer the PGIC questionnaire (Section 8.3).
- Administer the USP questionnaire (Section 9.6.2).
- Record any AEs that have occurred (Section 9.7).
- Determination of the CGIC by the Investigator (Section 8.2).
- Record all concomitant medications/therapies the subject is currently taking (Section 7.7).

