4 INVESTIGATIONAL PLAN

4.1 Overall Study Design

This is a multicenter, randomized, double-blind, placebo-controlled, parallel-group study to evaluate the safety and efficacy of oral AERT in MS patients with spasticity. Two doses of AERT, 40 mg and 80 mg, will be compared with placebo. The treatment groups will be randomized in a 1:1:1 ratio. There will be a 9-day titration period, then a 75-day maintenance period, followed by a 7-day taper period. Figure 1 presents the timeline diagram for the study. Figure 2 presents the blinded dosing regimen flowchart, including titration and taper doses, to be used during the study. The dosing schema is presented in Figure 3.

Eligible patients will undergo up to a 21-day washout period for withdrawal of all medications used for anti-spasticity and/or muscle relaxation prior to randomization. A baseline clinical evaluation will be performed (Visit 2) to confirm eligibility for study randomization, and subjects will be randomly assigned to 1 of 3 treatment arms: (1) AERT 40 mg; 2) AERT 80 mg; or 3) placebo. During the first 9 days of drug administration, doses will be titrated every 3 days to a fixed-dose of either AERT 40 mg, AERT 80 mg, or placebo. Subjects will remain at that fixed-dose for 75 days. The co-primary efficacy assessments, changes from baseline in the total numeric-transformed modified Ashworth Scale score of the most affected limb (TNmAS-MAL) and in the Clinical Global Impression of Change (CGIC), will be performed as shown in Table 1. At the end of the maintenance period, the subject's dose will be tapered for an additional 7 days before the subject returns to the site for a final safety evaluation at Day 92 (Visit 6). Table 1 describes the study visits and timing of all study procedures and assessments.

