1. Vital signs will be measured with the subject in a supine position and 3 minutes subsequently in a standing position after the supine assessment is completed. Body temperature and respiratory rate will be measured only during the supine assessment.
2. Premenopausal women of childbearing potential must have a negative serum pregnancy test within 21 days before Visit 2 (Baseline). Urine pregnancy testing will be performed at Visits 2 through 6.
3. The TNmAS-MAL assessment will be performed prior any scheduled lab draws and will always be done by the study evaluator (someone other than the investigator) who has been appropriately trained to perform and assess the TNmAS-MAL, and when possible all TNmAS-MAL assessments should be performed for a particular subject by the same study evaluator throughout the study. The most affected limb will be determined by the study evaluator.
4. Performed by the investigator or sub-investigator not functioning as the study evaluator for the particular subject.

Figure 1: Timeline Diagram, Study OS440-3004

6.1 Visit 1 (Screening) – Days –21 to 0

Each potential study subject will have a Screening visit (Visit 1) within 21 days prior to randomization at the Baseline visit (Visit 2). At Screening, the investigator will fully explain to the subject the objectives, characteristics, and procedures for the study. Rescreening of subjects will only be allowed for delays in screening (eg, >21 days) that have occurred due to technical errors (eg, issue with the Interactive Response Technology [IRT] system, or with delivery or assessment of laboratory tests, etc). Screening assessments/procedures will include the following:

- Obtain a signed and dated ICF from each subject prior to any study-specific procedures being conducted ([Section 13.3](#)).
- Assess eligibility according to the inclusion ([Section 5.1](#)) and exclusion criteria ([Section 5.2](#)).
- After establishing the subject's eligibility to participate, explain to the subject how to withdraw all anti-spasticity medication (up to a 21-day period) prior to the next visit ([Section 7.7](#)).
- Assignment of an enrollment number ([Section 7.4](#)).
- Record demographic data, including age, sex, race, and ethnicity.
- Record medical and surgical history ([Section 9.1](#)).
- Record physical examination results ([Section 9.3](#)).
- Record weight and height ([Section 9.4](#)).
- The study evaluator will perform the TNmAS-MAL ([Section 8.1](#)).

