- Record vital sign measurements, including blood pressure (BP), heart rate, respiratory rate, and body temperature ([Section 9.2](#)).
- Collect blood and urine samples for hematology, serum chemistry, and urinalysis ([Section 9.5](#)). Subject should be fasting if possible. As per Exclusion Criterion 12, if, in the opinion of the investigator, a subject has clinically significant abnormal laboratory value(s) at Visit 1 (Screening), they will be excluded from the study.
- Perform a standard 12-lead electrocardiogram (ECG) ([Section 9.6.1](#)).
- Collect a blood sample for serum pregnancy testing for women of childbearing potential. Because contraception is required throughout the study for both males and females, the use of an acceptable method throughout the study will be discussed with all subjects ([Section 7.8](#)).
- Administer the C-SSRS ([Section 9.6.3](#)).

- Administer the EDSS ([Section 8.4](#)).
- Administer the USP questionnaire ([Section 9.6.2](#)).
- Record all concomitant medications/therapies the subject is currently taking ([Section 7.7](#)).
- Schedule the next visit within approximately 7 to 14 days.

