6.2 Visit 2 (Baseline) – Day 1 (±3 days)

This visit takes place after the subject has completed withdrawal of all anti-spasticity medications. Assessments/procedures will include the following:

- Review eligibility according to the inclusion ([Section 5.1](#)) and exclusion criteria ([Section 5.2](#)).
- Review study discontinuation criteria ([Section 12.4](#)).
- Verify complete washout and abstinence from oral anti-spasticity medications for at least the past 14 days ([Section 7.7](#)).
- If the subject is eligible for randomization, obtain a randomization code and medication kit number for that subject ([Section 7.4](#)).
- The study evaluator will perform the TNmAS-MAL ([Section 8.1](#)).
- Record vital sign measurements, including BP, heart rate, respiratory rate, and body temperature ([Section 9.2](#)).
- Collect blood and urine samples for hematology, serum chemistry, and urinalysis ([Section 9.5](#)). Subject should be fasting if possible. As per Exclusion Criterion 12, if, in the opinion of the investigator, a subject has clinically significant abnormal laboratory value(s) at Visit 2 (Baseline), they will be excluded from the study.
- Collect a urine sample for pregnancy testing for women of childbearing potential ([Section 7.8](#)).
- Dispense the study medication. The Investigator will explain to the subject how to take the study medication and the regimen to be followed until the next visit ([Section 7.5](#)).
- The site will administer the first daily dose of study medication to the subject.
- Administer the C-SSRS ([Section 9.6.3](#)).
- Administer the EDSS ([Section 8.4](#)).
- Administer the USP questionnaire ([Section 9.6.2](#)).
- Record any adverse events (AEs) that have occurred ([Section 9.7](#)).

- Record all concomitant medications/therapies the subject is currently taking ([Section 7.7](#)).
- Schedule the next study visit.

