9.6 Other Assessments

9.6.1 Electrocardiograms

A standard 12-lead ECG will be performed on subjects in the supine position. Subjects will have rested in the supine position for at least 5 minutes prior to the ECG. The time at which the subject assumed the supine position will be recorded to confirm the rest time. ECGs will be done at the visits specified in Table 1.

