10.6. Other Safety Measures

C-SSRS results will be presented in subject data listings.

USP summary scores (stress urinary incontinence score, overactive bladder score, and low stream score) will be summarized descriptively for each treatment group by time point for the observed value as well as for the change from baseline value. All USP data (including the 10 individual questions) will be presented in listings.

ECG parameters will be summarized descriptively for each treatment group by time point for the observed value as well as for the change from baseline value. All ECG data will be presented in listings.

No other safety analyses have been prospectively defined. If, however, after study results are reviewed, or the DSMB or Sponsor recommend additional safety parameters or analyses be completed, they will be fully described and documented in the final clinical study report. The SAP does not need to be amended to complete any other safety measures identified as post-hoc.

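### No ECG is scheduled at the 40 or 80 mg/day maintenance dose, so for completers the planned ECG change-from-baseline summary cannot describe on-treatment effects

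*Protocol*

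**What the plan says.** Protocol Section 9.6.1 leaves the timing to the schedule: "ECGs will be done at the visits specified in Table 1". The ECG row of Table 1 has two marks, and the visit lists place them. Section 6.1 (Visit 1) has "Perform a standard 12-lead electrocardiogram (ECG" and Section 6.5 (Visit 6) has "Perform a standard 12-lead ECG (Section 9.6.1". Sections 6.2, 6.3 and 6.4, covering Visits 2 to 5, list none. SAP Table 1 carries the same row.

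On treatment timing, Protocol 4.1 states: "There will be a 9-day titration period, then a 75-day maintenance period, followed by a 7-day taper period". The dose is then "tapered for an additional 7 days before the subject returns to the site for a final safety evaluation at Day 92".

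On the baseline side, at Visit 1 the site is to "explain to the subject how to withdraw all anti-spasticity medication (up to a 21-day period) prior to the next visit". Of Visit 2 the protocol says: "This visit takes place after the subject has completed withdrawal of all anti-spasticity medications". The scheduled pre-dose ECG therefore comes before washout, and the post-washout, pre-dose visit has none.

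SAP 4.2.2 lists 12-lead ECGs among the safety endpoints, and SAP 10.6 gives the analysis: "ECG parameters will be summarized descriptively for each treatment group by time point for the observed value as well as for the change from baseline". SAP 7.3.3 assigns early-termination data to the closest scheduled visit, or to the next available visit if the closest already has valid data.

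**The concern.** The primary objective covers safety as well as efficacy, and ECG is a named safety assessment. A table of ECG change from baseline by treatment group will naturally be read as evidence about 40 and 80 mg/day. For completers, the post-baseline value in that table is planned for after the taper. An ECG effect that is present at the maintenance dose and reverses when dosing ends could leave no trace, and the table would look reassuring for a reason unrelated to the drug's effect at those doses.

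ECG is the exception among the safety assessments. Adverse events, vital signs, laboratory tests, the C-SSRS and the USP are all scheduled at Visits 3, 4 and 5. None of these records intervals or conduction. Neither document gives a reason for the ECG timing; Protocol 9.8 says only that the safety measures are standard.

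**Working it through.** **Inputs.** Titration 9 days, maintenance 75, taper 7 (Protocol 4.1); Visit 5 at Day 84 ±5 and Visit 6 at Day 92 ±5 (Protocol Table 1); about 170 subjects per arm (Protocol 5).

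**Step 1: reproduce the plan's Day 92.** Counting from Day 1:
- titration: Days 1 to 9
- maintenance: Days 10 to 84 (9 + 75 = 84)
- taper: Days 85 to 91 (84 + 7 = 91)
- first nominal day without study drug: 91 + 1 = Day 92, which matches the stated day of Visit 6.

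**Step 2: distance of the Visit 6 ECG from dosing.**
- from the last maintenance day: 92 − 84 = 8 days
- from the last taper day: 92 − 91 = 1 day

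**Step 3: scheduled ECGs by treatment phase, for a completer.**

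| Phase | Visits | Scheduled ECGs |
|---|---|---|
| Before washout | Visit 1 | 1 |
| After washout, before first dose | Visit 2 | 0 |
| After titration and through maintenance | Visits 3, 4, 5 | 0 |
| After taper (nominal) | Visit 6 | 1 |

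The maintenance-dose count is zero for all completers among the 2 × 170 = 340 subjects planned for the active arms.

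**Step 4: visit windows.** Visit 6 may fall on Days 87 to 97, which is 11 days. Days 87 to 91, 5 of the 11, lie within the nominal taper; Days 92 to 97 are 1 to 6 days after it. If the taper is assumed to start the day after the actual Visit 5 (Days 79 to 89), there are 11 × 11 = 121 date pairs. Six of these put Visit 6 on or before Visit 5, leaving 115, and in 49 of the 115 Visit 6 lands on a taper day. This counts permitted dates and does not estimate a share of subjects. It shows that some completers could have an ECG on a tapered dose, which is still not the 40 or 80 mg/day maintenance dose.

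**Step 5: early terminators.** They have the Visit 6 ECG at withdrawal, possibly while still on drug. SAP 7.3.3 then places it by calendar proximity. The midpoint of Days 42 and 84 is Day 63, and that of Days 84 and 92 is Day 88. An early-termination ECG between those midpoints would be assigned to Visit 5, an earlier one to an earlier visit, and a later one to Visit 6. It would thus sit at a visit with no scheduled ECG, or be pooled at Visit 6 with post-taper ECGs. Nothing in the SAP separates on-drug from off-drug ECGs.

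**Step 6: baseline.** The pre-washout reference matters only for subjects taking anti-spasticity medication at screening (Inclusion Criterion 6a); the documents do not give their share. Randomization should balance it across arms. It therefore blurs within-arm change but should not favor either side of an AERT-versus-placebo comparison.

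**The case against.** The strongest reply is that safety does not rest on the ECG. It is one of six safety components, and the other five are collected on treatment, including supine and standing heart rate and blood pressure. Protocol 9.7.1 also calls for all relevant evaluations when an adverse event is suspected. This stands. A reader might infer that the safety objective cannot be answered; the documents do not support that, because the gap is confined to the routine on-dose ECG. An event-prompted evaluation would, however, miss a silent change.

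A reader might also infer that no completer will ever have an ECG while taking AERT. That goes too far: the Visit 6 window overlaps the taper, even though Protocol 4.1 describes the return visit as following it. Nor can one say how much drug remains at Day 92, because the documents give no half-life for arbaclofen or for the extended-release tablet, and the dosing figures are not shown.

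It can further be said that the safety analysis is descriptive with no tests (Protocol 11.5), that the documents commit to no on-dose ECG conclusion, that they state no specific ECG concern, and that the Day 92 visit is openly described as after the taper. These points limit the seriousness. They do not change what the SAP 10.6 table can show, and the SAP does not label the completer values as post-taper.

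**Conclusion.** The point holds within limits. No ECG is scheduled at the maintenance dose, so for completers the SAP 10.6 summary cannot describe on-treatment ECG effects at 40 or 80 mg/day. An effect that persists after the taper could still be seen. Early terminators may supply some on-drug ECGs, but they are a selected group and the SAP does not identify those ECGs as on-drug.

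The pre-washout baseline is a secondary matter. It is a reason to read the ECG summary as AERT versus placebo and not as change within an arm.

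The conclusion rests on the nominal day count, which reproduces the plan's own Day 92, and on the agreement of both schedule tables with the visit lists. It needs no assumption about residual drug. It is a modest weakness in one safety component with an inexpensive remedy.

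**What to change.** - **Schedule.** In Protocol Table 1 and Sections 6.4 and 6.5, and in SAP Table 1, move the completer ECG from Visit 6 to Visit 5 (Day 84 ±5), before the first taper dose. Keep the ECG at Early Termination.
- **SAP 10.6.** Summarize ECG change at Visit 5 as on-treatment, compared between AERT and placebo. Exempt early-termination ECGs from the closest-visit rule in SAP 7.3.3, and show them separately by whether the subject was still taking study drug.
- **ECGs already taken at Day 92.** Label them post-taper and draw no on-treatment conclusion from them.

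The cost is a schedule amendment and a few lines of SAP text; the number of ECGs per subject is unchanged. The downside is that completers would have no end-of-study ECG after taper. The change leaves the pre-washout baseline as it is. An ECG at Visit 2 before the first dose would resolve that at one extra ECG per subject, but it is optional because the between-arm comparison should be balanced without it. If the schedule can no longer be changed, the separate display by drug status and the post-taper label can still be adopted in the SAP alone.

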7 STUDY TREATMENTS

7.1 Treatments Administered

Two doses of AERT, 40 mg (20 mg BID) and 80 mg (40 mg BID), and placebo. The description of study drug kits and treatments is shown below in Table 2.

Table 2: Study Drug Kits and Treatments, Study OS440-3004

Dosage form description:	
Package description:	
Daily dose:	There will be a 9-day titration period, then a 75-day maintenance period, followed by a 7-day taper period. Study tablets will be taken twice daily (BID). All subjects will take two tablets in the AM and 2 tablets in the PM. Post titration all subjects will take either placebo, 40 mg/day AERT, or 80 mg/day AERT.
Cumulative maximal dosage:	3320 mg (40 mg group) or 6580 mg (80 mg group) arbaclofen; 0 mg for placebo.
Manufacturer:	Osmotica Pharmaceutical US, Marietta, Georgia, USA

7.1.1 Treatment Administration

The study medications will be administered orally twice daily (every 12 hours, or BID) without regard to food.

Dose adjustments, except for those specified in the protocol during the titration and taper periods, are not permitted in this study. Subjects who require a dose adjustment or who discontinue study

drug for greater than 5 consecutive days must be withdrawn from the study and followed for safety ([Section 12.4](#)).

7.1.2 Labeling of Study Drug

Double-blind study medication will be provided in blister card wallets. The labels will include all information required by federal and local regulations.

7.1.3 Storage of Study Drug

Arbaclofen extended-release tablets and matching placebo tablets must be stored at 25°C (77°F); excursions permitted to 15-30°C (59-86°F) (see USP Controlled Room Temperature). Study medication should be protected from moisture and humidity. At study sites, all study medication must be stored, secured, and locked in a safe place.

7.2 Study Drug Accountability

The Principal Investigator will have overall responsibility for the use of the study drug. The Principal Investigator or designee will confirm receipt of the study drug by signature and date. A copy of this receipt must be returned to the Sponsor or designee when the contents of the drug shipment have been verified. In addition, an accurate study drug dispensing record that specifies the date and amount dispensed to each subject must be kept in accordance with the study drug accountability form. This inventory record must be available for inspection during an audit (eg, by Sponsor or a regulatory agency). At the conclusion of the study, the Principal Investigator must provide a copy of this record to the Sponsor.

Under no circumstances will the Investigator allow the investigational drugs to be used other than as directed by this protocol. The study medication must be protected from unauthorized access (eg, in a locked storage facility). Qualified study personnel must use the specified randomization system to assign subjects to treatment. Reasons for digression from the expected dispensing regimen must also be recorded.

At the end of the study all medication must be reconciled. Any unused medication will be inventoried by the Investigator or designee and retained by the site until instructed otherwise by Sponsor.

7.3 Handling and Disposal of Study Drug

The study drug must be protected from unauthorized access (eg, in a locked storage facility).

Any unused, partially used, or empty blister card wallets of study drug will be returned to the Sponsor or designee by the time of the site's close-out visit. Receipt, distribution, and return of the study drug must be properly documented on forms provided by the Sponsor or designee.

7.4 Method of Assignment of Study Drug

Two doses of AERT, 40 mg (20 mg BID) and 80 mg (40 mg BID), will be compared with placebo. The treatment groups will be randomized in a 1:1:1 ratio.

After Screening procedures have been completed, authorized site personnel will acknowledge that the applicable subject met all the specified inclusion criteria ([Section 5.1](#)) and none of the exclusion criteria ([Section 5.2](#)) and an enrollment number will be sequentially assigned. After the Screening clinical laboratory test results and other clinical assessments have been completed at Visit 2 (Baseline), assignment to a treatment group will then follow a predetermined list of randomization numbers, with each successive number receiving 1 of the 3 treatments in random order. Authorized site personnel will use the IRT system to assign a kit number that corresponds to the randomization schedule. The kit box with the assigned kit number will be dispensed to the subject.

The randomization code will be provided by the CRO.

7.5 Selection and Timing of Doses in the Study

There will be a 9-day titration period, then a 75-day maintenance period, followed by a 7-day taper period. Figure 2 presents the dosing regimen flowchart, including titration and taper doses, to be used during the study. The dosing schema is presented in Figure 3.

[figure not shown]
[figure not shown]

Figure 3: Dosing Schema, Study OS440-3004

7.6 Emergency Unblinding

This is a double-blind study. Every effort will be made to retain the integrity of the blind. The study drug will be identical in appearance for all subjects, regardless of treatment assignment, by using over-encapsulation of the different tablet strengths.

In the event that emergency identification of study drug is required (eg, if the Investigator believes that the information is necessary to properly treat a subject with an AE), the study drug identity can be obtained by the investigator directly accessing the IRT system. The subject should be informed of the treatment assignment.

Every effort must be made to alert the Medical Monitor before requesting that the blind be broken. If this is not possible, the Medical Monitor should be immediately notified of the breaking of the blind. The Investigator will record the unblinding procedures in the subject's source documents.

If unblinding is necessary, the subject will be withdrawn from the study and Visit 6 (Final or Early Termination Visit) procedures will be completed.

The study blind will be broken at study completion once the following are met:

- Database is locked
- The statistical analysis plan (SAP) is finalized

Once the decision for unblinding is reached, the study team will prepare an unblinding memo with signatures from the study director and sponsor biostatistician.

